9.5.2.2 Description of Procedures/Assessments Schedule

Please refer to [Table 2](#) and [Table 3](#) for the timings of the procedures and assessments to be performed during the study. Screening assessments will be organized into 5 tiers (see [Table 2](#)). See [Section 9.5.1](#) for a full description of the procedures and assessments to be performed during this study.

[Table 4](#) presents the number of blood and CSF samples, and the estimated total volume of blood and CSF that will be collected throughout the study. (revised per Amendment 03) Additional samples may be taken at the discretion of the investigator if the results of any tests fall outside reference ranges or if clinical symptoms necessitate testing to ensure subject safety. Actual specimen volumes may vary based on local regulations. (revised per Amendment 03)

Table 4 Summary of Estimated Blood and CSF Sample Volumes

Assessment	Total Number of Collection Time Points	Sample Volume, Number of Time Points × Volume per Collection (mL)		Total Volume ^a (mL)
		Screening Visits	Treatment and Follow-Up Periods	
Blood				
Clinical chemistry (revised per Amendment 03)	15	1×2.5 mL	14×2.5 mL	37.5 mL
Serum pregnancy test at Screening (females of child-bearing potential only)	1	can use blood drawn for clinical chemistry	none	no additional volume
Hematology	15	1×2 mL	14×2 mL	30 mL
Coagulation (revised per Amendment 03)	15	1×1.8 mL	14×1.8 mL	27 mL
Thyroid function tests (thyroid stimulating hormone, free triiodothyronine and free thyroxine)	1	1×5 mL	none	5 mL
Viral screen at Screening (Hepatitis B and C) (revised per Amendment 03)	1	1×2.5 mL	none	2.5 mL
Viral characterization at Visit 2 (previous exposure to CMV, HSV1, HSV2, etc.) (revised per Amendment 03)	1	None	1×3.5 mL	3.5mL
Vitamin B12 at Screening (revised per Amendment 03)	1	can use blood drawn for TFT	none	no additional volume
Blood for immunologic assessments, including isolation of PBMCs for storage and later testing (revised per Amendment 01)	15	1×20 mL	14×20 mL	300 mL
Blood for immune status	8	none	8×5 mL	40 mL
PD and exploratory biomarker sample (revised per Amendments 02 and 03)	10	1×24 mL	9×6 mL	78 mL
PK analysis (revised per Amendments 02 and 03)	7	none	14×2 mL	28 mL
Pharmacogenomic sample (revised per Amendment 03)	1	1×6 mL	none	6 mL
All blood samples, total volume collected (revised per Amendments 02 and 03)		61.3 mL	458.7 mL	520 mL
CSF				
Amyloid eligibility	1	1×12 mL	none	12 mL
PD / PK (optional longitudinal substudy)	1	none	1×12 mL	12 mL

CMV = cytomegalovirus, CSF = cerebrospinal fluid, HSV1 = herpes simplex virus 1 (orolabial herpes), HSV2 = herpes simplex virus 2 (genital herpes), PBMCs = peripheral blood mononuclear cells, PD = pharmacodynamics, PK = pharmacokinetic, TFT = thyroid function Test.

a: The total volume includes all blood/CSF collection from Screening through Week 117 (Followup Visit); actual volume may vary based on local regulations. (revised per Amendment 03)

9.5.3 Appropriateness of Measurements

All clinical assessments are standard measurements commonly used in studies of AD.

Standard safety assessments incorporated into this protocol include assessment of AEs and SAEs, measurement of vital signs, clinical laboratory assessments, physical examinations (including dermatologic review), neurologic examinations, ECG measurements, assessments of suicidal thinking and behavior, and MRI.

9.5.4 Reporting of Serious Adverse Events, Pregnancy, and Events Associated with Special Situations

9.5.4.1 Reporting of Serious Adverse Events

All SAEs, regardless of their relationship to study treatment, must be reported on a completed SAE form by email or fax as soon as possible but no later than 24 hours from when the investigator becomes aware of the event.

SAEs, regardless of causality assessment, must be collected up to 12 weeks after the last dose of study drug. All SAEs must be followed to resolution or, if resolution is unlikely, to stabilization. Any SAE judged by the investigator to be related to the study treatment or any protocol-required procedure should be reported to the sponsor regardless of the length of time that has passed since study completion.

The detailed contact information for reporting of SAEs is provided in the Investigator Study File.

For urgent safety issues, please ensure all appropriate medical care is administered to the subject and contact the appropriate study team member listed in the Investigator Study File.

It is very important that the SAE report form be filled out as completely as possible at the time of the initial report. This includes the investigator's assessment of causality.

Any follow-up information received on SAEs should be forwarded within 1 business day of its receipt. If the follow-up information changes the investigator's assessment of causality, this should also be noted on the follow-up SAE form.

Preliminary SAE reports should be followed as soon as possible by detailed descriptions including copies of hospital case reports, autopsy reports, and other documents requested by the sponsor.

The investigator must notify his/her IRB/IEC of the occurrence of the SAE in writing, if required by their institution. A copy of this communication must be forwarded to the sponsor, or its designee, to be filed in the sponsor's Trial Master File.

9.5.4.2 Reporting of Pregnancy and Exposure to Study Drug Through Breastfeeding

Any pregnancy in which the estimated date of conception is either before the last visit or within 28 days of last study treatment, or any exposure to study drug through breastfeeding during study treatment or within 28 days of last study treatment, must be reported.

If an adverse outcome of a pregnancy is suspected to be related to study drug exposure, this should be reported regardless of the length of time that has passed since the exposure to study treatment.

A congenital anomaly, death during perinatal period, an induced abortion, or a spontaneous abortion are considered to be an SAE and should be reported in the same time frame and in the same format as all other SAEs (see Reporting of SAEs [[Section 9.5.4.1](#)]).

Pregnancies or exposure to study drug through breastfeeding must be reported by fax or email as soon as possible but no later than 1 business day from the date the investigator becomes aware of the pregnancy. The contact information for the reporting of pregnancies and exposure to study drug through breastfeeding is provided in the Investigator Study File. The Pregnancy Report Form must be used for reporting. All pregnancies must be followed to outcome. The outcome of the pregnancy must be reported as soon as possible but no later than 1 business day from the date the investigator becomes aware of the outcome.

A subject who becomes pregnant must be withdrawn from study treatment.

9.5.4.3 Reporting of Events Associated with Special Situations

9.5.4.3.1 REPORTING OF ADVERSE EVENTS ASSOCIATED WITH STUDY DRUG OVERDOSE, MISUSE, ABUSE, OR MEDICATION ERROR

AEs associated with study drug overdose, misuse, abuse, and medication error refer to AEs associated with uses of the study drug outside of that specified by the protocol. Overdose, misuse, abuse, and medication error are defined as follows:

Overdose	Accidental or intentional use of the study drug in an amount higher than the protocol-defined dose
Misuse	Intentional and inappropriate use of study drug not in accordance with the protocol
Abuse	Sporadic or persistent intentional excessive use of study drug accompanied by harmful physical or psychological effects
Medication error	Any unintentional event that causes or leads to inappropriate study drug use or subject harm while the study drug is in the control of site personnel or the subject.

All AEs associated with overdose, misuse, abuse, or medication error should be captured on the Adverse Event eCRF and also reported using the procedures detailed in Reporting of SAEs (Section 9.5.4.1) even if the AEs do not meet serious criteria. Abuse is always to be captured as an AE. If the AE associated with an overdose, misuse, abuse, or medication error does not meet serious criteria, it must still be reported using the SAE form and in an expedited manner but should be noted as nonserious on the SAE form and the Adverse Event eCRF.

9.5.4.3.2 REPORTING OF STUDY-SPECIFIC EVENTS

Study-specific events (as detailed in Section 9.5.1.5.2) should always be considered as serious important medical events and be entered on the Adverse Event eCRF and reported using the procedures detailed in Reporting of SAEs (Section 9.5.4.1), even if the study-specific event does not meet other serious criteria.

9.5.4.4 Expedited Reporting

The sponsor must inform investigators (or as regionally required, the head of the medical institution) and regulatory authorities of reportable events, in compliance with applicable regulatory requirements, on an expedited basis (ie, within specific time frames). For this reason, it is imperative that sites provide complete SAE information in the manner described above.

9.5.4.5 Breaking the Blind

In the case of a medical emergency where the appropriate treatment of the subject requires knowledge of the study treatment given, the investigator may break the randomization code for an individual subject. In all such cases, the AE necessitating the emergency blind break will be handled as an SAE in accordance with the procedures indicated above. Any broken code will be clearly justified and documented. The medical monitor must be notified immediately of the blind break.

9.5.4.6 Regulatory Reporting of AEs

AEs will be reported by the sponsor or a third party acting on behalf of the sponsor to regulatory authorities in compliance with local and regional law and established guidance. The format of these reports will be dictated by the local and regional requirements.

All studies that are conducted within any European country will comply with European Good Clinical Practice Directive 2005/28/EC and Clinical Trial Directive 2001/20/EC. All SUSARs will be reported, as required, to the competent authorities of all involved European member states.

9.5.5 Completion/Discontinuation of Subjects

A subject may elect to withdraw from the study at any time for any reason. All subjects who discontinue study drug early for any reason will undergo an ED Visit within 7 days of their

last dose of study drug (see [Section 9.1.2.2](#)). In addition, Follow-Up Visits will be scheduled 4 and 12 weeks after the last dose of study drug (Visit 14 and Visit 15, respectively) (see [Section 9.1.2.2](#)). These Follow-Up Visits will be conducted to monitor efficacy and safety parameters after early withdrawal from the study or discontinuation of study drug. See [Table 3](#) for full details of the assessments to be performed at these visits.

All subjects who discontinue study drug before reaching 12 months of treatment will also be asked to return to the clinic for a 12 month clinical assessment and then again at 24 months. Subjects who discontinued treatment between 12 and 24 months of treatment will be asked to return to the clinic for a 24 month clinical assessment. Subjects who discontinue early from study drug are considered “on study” as long as they continue to return for their clinical assessments at 12 and 24 months as outlined above, at which efficacy and quality of life will be assessed along with concomitant medications and AEs. However, subjects who discontinue study drug early are not considered to have ‘completed’ the study as a final Subject Disposition. A subject removed from the study for any reason may not be replaced.

The investigator will promptly explain to the subject involved that the study will be discontinued for that subject and provide appropriate medical treatment and other necessary measures for the subject. A subject who has ceased to return for visits will be followed up by mail, phone, or other means to gather information such as the reason for failure to return, the status of treatment compliance, the presence or absence of AEs, and clinical courses of signs and symptoms.

The primary reasons for early withdrawal from the study are: AE, lost to follow-up, subject choice, withdrawal of consent, pregnancy, study terminated by sponsor, and other. The secondary reasons for early withdrawal from the study are: AE, subject choice, and other.

The primary reasons for early discontinuation from the study drug are: AE, subject choice, pregnancy, inadequate therapeutic effect, and other. The secondary reasons for early discontinuation from the study drug are: AE, subject choice, inadequate therapeutic effect, and other.

9.5.6 Abuse or Diversion of Study Drug

AEs associated with abuse or diversion will be appropriately reported as AEs and monitored per [Section 9.5.1.5.1](#). Abuse is always to be captured as an AE.

During the study, the investigator should be aware of the possibility of abuse or diversion of study drugs and should report any concern about mishandling, abuse, loss, theft, or diversion of study drugs by completing the Abuse or Diversion of Study Drug eCRF.

9.5.7 Confirmation of Medical Care by Another Physician

The investigator will instruct subjects to inform site personnel when they are planning to receive medical care by another physician. At each visit, the investigator will ask the subject whether he or she has received medical care by another physician since the last visit or is

planning to do so in the future. When the subject is going to receive medical care by another physician, the investigator, with the consent of the subject, will inform the other physician that the subject is participating in the clinical study.

9.6 Data Quality Assurance

This study will be organized, performed, and reported in compliance with the protocol, standard operating procedures, working practice documents, and applicable regulations and guidelines. Site audits will be made periodically by the sponsor's or the CRO's qualified compliance auditing team, which is an independent function from the study team responsible for conduct of the study.

9.6.1 Data Collection

Data required by the protocol will be collected on the eCRFs and entered into a validated data management system that is compliant with all regulatory requirements. As defined by ICH guidelines, the CRF is a printed, optical, or electronic document designed to record all of the protocol-required information to be reported to the sponsor on each study subject.

Data collection on the eCRF must follow the instructions described in the CRF Completion Guidelines. The investigator has ultimate responsibility for the collection and reporting of all clinical data entered on the eCRF. The investigator or designee as identified on Form FDA 1572 (where applicable) must sign the completed eCRF to attest to its accuracy, authenticity, and completeness.

Completed, original eCRFs are the sole property of Eisai and should not be made available in any form to third parties without written permission from Eisai, except for authorized representatives of Eisai or appropriate regulatory authorities.

9.6.2 Clinical Data Management

All software applications used in the collection of data will be properly validated following standard computer system validation that is compliant with all regulatory requirements. All data, both eCRF and external data (eg, laboratory data), will be entered into a clinical system.

Electronic source (eSource) methodology may be used for some of the clinical efficacy and HRQoL assessments performed in this study.

9.7 Statistical Methods

All statistical analyses will be performed by the sponsor or designee. Statistical analyses will be performed using SAS software or other validated statistical software as required.

All statistical tests will be based on the 5% (2-sided) level of significance, unless specified.

9.7.1 Statistical and Analytical Plans

All statistical analyses will be performed by the Sponsor or designee after the study is completed and the database is locked and released for unblinding.

9.7.1.1 Study Endpoints

9.7.1.1.1 PRIMARY ENDPOINT

The primary endpoint of the study is:

- Change from baseline in the CDR-SB at 24 months.

9.7.1.1.2 SECONDARY ENDPOINTS

The secondary endpoints of the study are:

- Time to worsening of CDR scores by 24 months (eg, the worsening of global CDR score is defined as an increase from baseline by at least 0.5 points on the global CDR scale on 2 consecutive scheduled visits at which global CDR is undertaken)
- Time to conversion to dementia for subjects who were not clinically staged as dementia at Baseline based on clinical diagnosis
- The rate of change over time (mean slope) based on CDR-SB score over 24 months
- Change from baseline in CDR-SB at 27 months (ie, 24 months of treatment plus 3 months posttreatment follow-up) (revised per Amendment 01)
- Change from baseline in ADAS-cog₁₄, MMSE, and FAQ at 24 months
- Change from baseline in ADAS-cog₁₄ Word List (immediate recall and delayed recall) at 24 months (revised per Amendment 01)

9.7.1.1.3 EXPLORATORY ENDPOINTS

The exploratory endpoints of the study are:

- Time to change of concomitant AD treatment (ie, dose increase and/or initiation of treatment with AChEI or memantine after randomization) by 24 months
- The proportion of subjects at 24 months who received dose increases and/or initiation of treatment with AChEI or memantine after randomization
- The rate of change over time (mean slope) based on NPI-10 item score over 24 months
- Change from baseline in NPI-10 item at 24 months

- Change from baseline in EQ-5D (subject self-reported, study partner self-reported, and subject measured by proxy) and QOL-AD (subject and study partner) at 24 months
- Change from baseline in Zarit's Burden Interview at 24 months

9.7.1.1.4 BIOMARKERS ENDPOINTS

The biomarker endpoints for this study are:

- Change from baseline in amyloid PET SUVR composite at 24 months for brain amyloid levels
- Change from baseline in CSF biomarkers t-tau and p-tau at 24 months
- Change from baseline in CSF amyloid biomarkers A β (1-40), A β (1-42), and A β (1-x) at 24 months
- Change from baseline in total hippocampal volume at 24 months using vMRI (revised per Amendment 01)
- Change from baseline in the preservation of connectivity on fMRI at 24 months

9.7.1.2 Definitions of Analysis Sets

- The Randomized Set is the group of subjects who are randomized to study drug.
- The Safety Analysis Set is the group of subjects who receive at least 1 dose of study drug and have at least 1 postdose safety assessment.
- The Full Analysis Set (FAS) is the group of randomized subjects who receive at least 1 dose of study drug and have baseline and at least 1 postdose primary efficacy measurement.
- The Per Protocol Analysis Set (PPS) is the subset of subjects in the FAS who sufficiently comply with the protocol. The PP Analysis Set will be used to conduct a sensitivity analysis of the primary efficacy endpoint. Details of the evaluability criteria will be determined before database lock and treatment unblinding, and will be specified in the statistical analysis plan.
- The PK Analysis Set is the group of subjects with at least 1 quantifiable elenbecestat (E2609) plasma concentration with a documented dosing history.
- The PD Analysis Set is the group of subjects who have sufficient PD data to derive at least 1 PD parameter.

9.7.1.3 Subject Disposition

The number of subjects screened, the number (percent) of subjects who failed screening, and the reasons for screen failure will be summarized, based on data reported on the Screening Disposition eCRF. The distribution of the number of randomized subjects enrolled by each site will be summarized for each randomized treatment group. The primary reasons for

screen failures (did not meet inclusion or met exclusion criteria, AE, lost to follow-up, withdrawal of consent, and other) will be presented.

Study Completion: the number (percent) of randomized and treated subjects who completed the study and who discontinued from the study will be summarized according to the primary reason for discontinuation and secondary reason(s) for discontinuation, based on data reported on the Subject Disposition (Study Phase) CRF. The number (percent) will be presented by treatment group and total for subjects; randomized, not treated, treated, who completed the study, and discontinued from the study. The primary reasons for early withdrawal from the study are: AE, lost to follow-up, subject choice, withdrawal of consent, pregnancy, study terminated by sponsor, and other. The secondary reasons for early withdrawal from the study are: AE, subject choice, and other.

Completion of Study Treatment: the number (percent) of randomized and treated subjects who completed study drug and who discontinued from study drug will be summarized according to the primary reason for discontinuation and also according to secondary reason(s) for discontinuation, based on data reported on both the Subject Disposition (Study Phase) eCRF and ED from Study Drug eCRF. The number (percent) will be presented by treatment group and total for subjects; randomized, not treated, treated, who completed study drug, and discontinued from study drug. The primary reasons for early discontinuation from the study drug are: AE, subject choice, pregnancy, inadequate therapeutic effect, and other. The secondary reasons for early discontinuation from the study drug are: AE, subject choice, inadequate therapeutic effect, and other.

9.7.1.4 Demographic and Other Baseline Characteristics

Demographic and other baseline characteristics for the Safety Analysis Set and FAS will be summarized for each treatment group using descriptive statistics. Continuous demographic and baseline variables include age, CDR scores, ADAS-cog₁₄, MMSE and FAQ; categorical variables include sex, age group (equal or less than 65 years, age greater than 65 years), race, ethnicity, region, *ApoE4* genotype, prior treatment with AChEIs or memantine (no or yes), and clinical subpopulation (MCI due to AD or the early stages of mild AD). (revised per Amendment 01)

9.7.1.5 Prior and Concomitant Therapy

All investigator terms for medications recorded in the eCRF will be coded to an 11-digit code using the World Health Organization Drug Dictionary (WHO DD) (Mar 2014). The number (percentage) of subjects who took prior and concomitant medications will be summarized on the Safety Analysis Set by treatment group, Anatomical Therapeutic Chemical class, and WHO DD preferred term (PT). Prior medications will be defined as medications that stopped before the first dose of study drug. Concomitant medications will be defined as medications that (1) started before the first dose of study drug and were continuing at the time of the first dose of study drug, or (2) started on or after the date of the first dose of study drug up to the date of the last dose. All medications will be presented in subject data listings.

Medications taken within the 12-week Follow-Up Period will also be recorded.

9.7.1.6 Efficacy Analyses

The FAS will be used as the primary population for all efficacy analyses, while the PPS will be used as the supportive population.

9.7.1.6.1 PRIMARY EFFICACY ANALYSIS

The primary analysis will be based on an intent to treat philosophy without regard to adherence to treatment. The primary analysis of the change from baseline in CDR-SB at 24 months will be performed to compare elenbecestat (E2609) 50 mg per day versus placebo using a linear mixed effects model for repeated measures (MMRM) on the FAS. The MMRM model will include baseline CDR-SB as a covariate, with treatment group, visit, randomization stratification variables (ie, region [7 levels], clinical dementia [yes, no], and concurrent AD medication use at randomization (Visit 2) [yes, no]), and treatment group-by-visit interaction as fixed effects. (revised per Amendments 01 and 02) An unstructured covariance matrix will be employed to model the covariance of within subject effect; if MMRM fails to converge then a covariance structure with fewer parameters from the following list will be employed according to the prespecified order in the list until the MMRM converges. The list of covariance structure will include Heterogeneous Toeplitz, Toeplitz, Heterogeneous Compound Symmetry, and Compound Symmetry. This primary analysis will include all observed post baseline data of the change from baseline in CDR-SB without imputation of missing values. The treatment effect for elenbecestat (E2609) versus placebo will be compared at 24 months based on MMRM model. The LS means and difference in LS means between elenbecestat (E2609) treatment group and placebo, and corresponding 95% CI will be presented.

The null hypothesis is that there is no difference in the mean change from baseline in CDR-SB at 24 months between elenbecestat (E2609) 50 mg per day and placebo. The corresponding alternative hypothesis is that there is a difference in the mean change from baseline in CDR-SB at 24 months between elenbecestat (E2609) 50 mg per day and placebo.

The primary analysis will be repeated to minimize the impact of change in concomitant AD medications where efficacy data after initiation of new AD medications and increase of current AD medications will be censored.

The following sensitivity analysis will be conducted to evaluate the impact of missing data: the primary endpoint will be analyzed using ANCOVA after multiple imputation. The ANCOVA model will include baseline CDR-SB as a covariate, with treatment group and randomization stratification variables as factors.

Subgroup analysis (eg, *ApoE4* genotype) and additional sensitivity analysis for the primary endpoint will be performed as appropriate. (revised per Amendment 01)

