The other continuous secondary efficacy endpoints as defined above will be analyzed using the same MMRM model as the primary efficacy analysis to compare elenbecestat (E2609) 50 mg per day versus placebo on the FAS, using baseline value corresponding to the response variable in the model.

The relationship between clinical changes at 24 months (CDR-SB, ADAS-cog₁₄, MMSE, and FAQ) and changes in each of the biomarkers (amyloid PET, CSF t-tau and p-tau, vMRI, and fMRI) at 24 months, will be evaluated using an ANCOVA model. (revised per Amendment 01) Changes in clinical scales at 24 months will be the response variables and either continuous or categorical change of biomarkers will be independent variables. The ANCOVA model will also include baseline value for clinical scale as a covariate,

randomization stratification variables, treatment group as factors, and other terms as appropriate.

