9.7.2 Determination of Sample Size

The sample size for this study is estimated based on comparison of elenbecestat (E2609) versus placebo with respect to the primary efficacy endpoint, the change from baseline CDR-SB at 24 months. Based on available ADNI data [amyloid positive, MMSE equal or greater than 24, late MCI (global CDR=0.5) populations from ADNI, ADNI 2 and ADNI GO] the mean and the standard deviation of the change from baseline in the CDR-SB at 24 months in the placebo group are assumed to be 1.75 and 2.05, respectively. Therefore, assuming a 25% reduction in the mean change from baseline CDR-SB at 24 months for the elenbecestat (E2609) 50 mg per day dose group compared to placebo with a common standard deviation of 2.05 and an estimated 30% dropout rate in this study, a total sample size of 1330 subjects, 665 subjects in each treatment group, will be required to detect the treatment difference between elenbecestat (E2609) 50 mg per day and placebo using a 2-sample t-test with 90% power at a significance level of 2-sided alpha =0.05.

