The CDR will be conducted every 3 months during the Core Study; other cognitive and functional assessment instruments will be administered every 6 months. Every 3 months, the investigator is required to confirm the clinical staging of AD (ie, dementia or nondementia). This staging decision will be verified via a central review process and adjudicated if necessary (adjudication will only occur when there is a discrepancy between the clinical disease staging made by the site compared to that determined by the central review process; moreover, where adjudication is required, it will be undertaken by an independent assessor(s)). (revised per Amendment 01)

The health-related quality of life measures will be conducted every 6 months during the Core Study, along with the NPI-10.

MRI scans (including vMRI and fMRI) will be performed at 12 and 24 months during the Core Study or at the ED visit.

At every visit, AEs will be assessed, concomitant medications will be reviewed, physical examinations with dermatologic review by the study investigator will be performed, vital signs and respiratory rate will be measured, suicidality will be assessed, blood will be drawn for clinical chemistry, hematology, and for immunologic assessments. A urine sample will be provided for dipstick urinalysis. (revised per Amendment 01) Other assessments, including safety assessments (neurologic exams, ECGs, urine pregnancy tests for females of child-bearing potential), and blood draws for PK, PD and assessment of immune status are performed at different intervals throughout the treatment period of the study.

For subjects who consent to the amyloid PET longitudinal substudy, amyloid PET will be conducted after 12 and 24 months of treatment during the Core Study (or at the ED visit, provided the subject has received at least 39 weeks of study drug). For subjects who consent to the CSF longitudinal substudy, CSF will be collected after 24 months of treatment during the Core Study (or at the ED visit, provided the subject has received at least 39 weeks of study drug). Note that subjects who are assessed by both amyloid PET and CSF A β (1-42) are required to wait for a minimum of 48 hours between the 2 procedures. (revised per Amendment 02) Please refer to Schedule of Assessments ([Table 3](#)).

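### A baseline CDR-SB-by-visit term in the primary MMRM would be a nearly free improvement: the single baseline slope may lose some precision at month 24

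*Protocol*

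**What the plan says.** Section 9.7.1.6.1 lists the fixed effects in full: "The MMRM model will include baseline CDR-SB as a covariate, with treatment group, visit, randomization stratification variables" (region, clinical dementia, concurrent AD medication), "and treatment group-by-visit interaction as fixed effects". No other interaction is named. On the covariance it says: "An unstructured covariance matrix will be employed to model the covariance of within subject effect", with a fallback list if the model does not converge. On the data: "This primary analysis will include all observed post baseline data of the change from baseline in CDR-SB without imputation of missing values".

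Section 9.1.2.1 sets the visits: "The CDR will be conducted every 3 months during the Core Study". That gives eight post-baseline assessments up to month 24. Section 9.7.1.6.2 carries the model over: the remaining continuous secondary endpoints "will be analyzed using the same MMRM model as the primary efficacy analysis", each with its own baseline.

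The same primary section plans a missing-data sensitivity analysis of the month-24 endpoint, an ANCOVA after multiple imputation with baseline CDR-SB as covariate. Section 9.7.2 sizes the trial with a two-sample t-test that uses no covariate.

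**The concern.** A covariate entered only as a main effect has the same coefficient at month 3 as at month 24. In a progressive disease, baseline severity may say little about change over three months and more about change over two years. When one slope has to serve all visits, generalised least squares weights it towards visits with small residual variance. If variance grows with time, those are the early visits. The fitted slope can then sit well below the month-24 slope, and the decisive visit is under-adjusted.

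Two things could be at stake. One is precision that the baseline measurement could have bought at no cost. The other arises only if dropout depends on baseline severity in one arm and not the other: a wrong baseline slope at month 24 then no longer cancels between arms, and the contrast can shift.

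**Working it through.** **The plan's own figure.** From section 9.7.2, mean and SD "in the placebo group are assumed to be 1.75 and 2.05, respectively", and the effect follows from "assuming a 25% reduction in the mean change from baseline CDR-SB at 24 months": 0.25 × 1.75 = 0.4375.

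- n per arm = 2 × (2.05/0.4375)² × (1.960 + 1.282)² ≈ 462. With 30% dropout, 462/0.70 = 660 per arm, 1320 in total. The plan's 1330 reproduces within 1%.
- At 665 × 0.70 = 465.5 evaluable per arm, SE = 2.05 × √(2/465.5) = 0.1344 and 0.4375/0.1344 = 3.256. Power = Φ(3.256 − 1.96) = 90.2% with no covariate.

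**Assumed inputs.** The protocol gives no baseline-change correlation r, no visit-specific variances and no covariance. Take baseline SD 1, so the true month-24 slope is 2.05r.

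**Formulas.** Relative to no covariate, the month-24 variance ratio is 1 − r² with baseline-by-visit, and 1 − r² + (b24 − bc)²/2.05² with one common slope bc. Power = Φ(3.256/√ratio − 1.96).

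**An example that can be checked by hand.** Let residual change accumulate in independent increments, so that its covariance is proportional to the earlier of the two times. The GLS weights then fall wholly on the first visit, and bc equals the month-3 slope. Take r = 0.3, so b24 = 0.615 and month 3 is 1/8 of the way. The interaction model has ratio 0.910 and power Φ(3.413 − 1.96) = 92.7%.

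| Baseline slope over time (as a fraction of b24) | bc | Ratio, common slope | Covariate benefit kept | Power, common slope |
|---|---|---|---|---|
| Flat | 0.615 | 0.910 | 100% | 92.7% |
| Half present at the start, 0.5 + 0.5t | 0.346 | 0.927 | 81% | 92.2% |
| Grows as √t | 0.217 | 0.948 | 58% | 91.7% |
| Linear from zero | 0.077 | 0.979 | 23% | 90.8% |
| Slightly negative early, (t − 0.15)/0.85 | −0.018 | 1.005 | about −6% | 90.1% |

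For the linear row: 0.91 + (0.615 − 0.077)²/4.2025 = 0.91 + 0.069 = 0.979.

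The covariance matters as much as the shape. With constant variance and correlation 0.6 between visits, linear growth keeps 81% of the benefit.

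**Range over five slope shapes and four covariance structures** (common slope, then with interaction):

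- r = 0.1: 90.2–90.5%, then 90.5%
- r = 0.2: 90.1–91.4%, then 91.4%
- r = 0.3: 90.0–92.7%, then 92.7%

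The largest gain for r up to 0.3 is 92.7 − 90.0 = 2.7 points.

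**Simulation, dropout unrelated to baseline or outcome** (N = 1330, 30% monotone dropout, 400 trials per shape, r = 0.3). Month-24 variance relative to no covariate, common slope against interaction: linear 0.98 v 0.92; early negative 1.00 v 0.94; √t 0.96 v 0.94; flat 0.94 v 0.94. Mean estimates were −0.43 to −0.45 in every fit, against a true −0.4375, so no bias appeared.

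**Simulation, dropout rising with baseline severity in the active arm only** (28–29% monotone dropout, linear growth of the baseline effect).

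- Log-odds 0.8 per baseline SD, r = 0.3, 150 trials per scenario: common slope −0.51 to −0.53, interaction −0.44 to −0.45, true −0.4375.
- Log-odds 0.4, r = 0.2 to 0.3: the common slope moved by about 0.03 to 0.045 relative to the interaction model.

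Taken together, the shift is about 0.03 to 0.1 points, or 7% to 23% of the 0.4375 design effect. In these runs it favoured the drug.

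**The case against.** The case for leaving the model alone is substantial. A common baseline slope with visit, treatment-by-visit and unstructured covariance is a valid prespecified analysis, and the section is internally consistent. The sample size takes no credit for the covariate. Entry requires a global CDR of 0.5 and an MMSE of at least 24, and mild dementia is capped at about 25%, which narrows the baseline spread. The model already adjusts for clinical dementia, so what counts is the correlation left after that term, and it may be smaller than the values assumed here. The planned ANCOVA already fits a month-24-specific slope. All of this stands. It limits the size of the point, but it gives no reason to prefer the restricted model.

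Stronger readings are tempting and not supported:

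- A reader might infer that the covariate achieves almost nothing at month 24. That needs a baseline effect starting near zero or below and growing while the variance also grows. Other plausible patterns keep most or all of the benefit, and the protocol does not show which applies.
- A reader might convert the loss into a number of wasted subjects. Any such count rests on an unstated correlation and shape.
- A reader might conclude that the primary estimate is biased or the type I error inflated. Bias appeared only under assumed baseline-dependent dropout that differed by arm. In 250 null trials at the stronger dependence (r = 0.3), rejection was 12.4% against 6.0% with the interaction. At the weaker dependence the two models could not be told apart within simulation noise. The protocol has safety-driven discontinuation rules that could act unequally by arm, but nothing says they will act through baseline severity.

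**Conclusion.** The point holds as a low-severity, nearly free improvement. The model as written imposes one baseline slope on eight visits. Relaxing it is never less efficient in large samples. The precision at stake is 0 to about 2.7 power points for correlations of 0.1 to 0.3, and at r = 0.1 it is at most about 0.3. These figures rest on assumed correlations, slope shapes and covariances. Planned power stays at about 90% even where the common slope recovers nothing. The possible bias of about 0.03 to 0.1 points is conditional on dropout that depends on baseline differently by arm. The interaction largely removes it when recorded baseline explains that dropout.

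**What to change.** Before unblinding, add baseline CDR-SB-by-visit to the fixed effects of the primary MMRM. Add the corresponding baseline-by-visit term to the secondary MMRMs that reuse it: ADAS-cog14 and its word-list scores, MMSE, FAQ, and CDR-SB at 27 months. The size of the gain was worked out for the primary endpoint only; most of the secondary scales are assessed every six months, so their figures would differ.

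The cost is a line of text and 8 − 1 = 7 further parameters in the primary model, on about 1330 subjects. A side benefit is that the primary model and the ANCOVA sensitivity analysis would both allow a baseline slope specific to month 24. A difference between them would then reflect the handling of missing data and not also a different covariate adjustment. A clinical-dementia-by-visit term is optional, since its effect was not calculated.
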